### HOW SUPPLIED

SUFENTA (sufentanil citrate) injection is supplied as a sterile aqueous preservative-free solution for intravenous and epidural use as:

NDC 11098-050-01 50 µg/mL sufentanil base, 1 mL ampoules in packages of 10

NDC 11098-050-02 50 µg/mL sufentanil base, 2 mL ampoules in packages of 10

NDC 11098-050-05 50 µg/mL sufentanil base, 5 mL ampoules in packages of 10

Protect from light. Store at controlled room temperature (59°-77°/15°-25°C).

U.S. Patent No. 3,938,834

MAY 1995, SEPTEMBER 1995

Decatur, IL 62522

SFAON Rev. 10/01

This is a multicenter, open-label, single treatment clinical study designed to evaluate the overall functionality of the Zalviso System (sufentanil sublingual tablet system) 15 mcg for the treatment of acute moderate-to-severe postoperative pain.

The study was designed to demonstrate that the device dispense failure rate is non-inferior to a target of 2%. This is based on the criteria that the upper limit of a 90% confidence interval (CI) of the device dispense failure rate is not worse than 5%.

The statistical issues regarding the conduct and analysis of this study are described briefly in the following sections.

2 Statistical Methods

2.1 Determination of Sample Size

A sample size of approximately 330 patients is planned for this study in order to have at least 315 patients receive study drug and have available efficacy data for data analysis.

A sample size of 315 patients will have 90% power to demonstrate that the device dispense failure rate is non-inferior to a target of 2%. This failure rate is the proportion of patients who experienced at least one of following events: (1) a system-generated error, (2) a tablet dispensed but not requested, or (3) a tablet dispensed when the Zalviso System is in lockout. All events listed above will be obtained from the Controller patient usage data.

This is based on the criteria that the upper limit of a 90% confidence interval (CI) of the device dispense failure rate is not worse than 5%. This calculation is based on the exact binomial test of one-sample proportion for a one-sided case against a 2% target proportion with a delta of 3%, and a one-sided significance level of $\alpha=0.05$. This sample size was generated from the SAS procedure PROC POWER for one-sample proportion. Exact power computations are based on the binomial distribution and computing formulas provided by Johnson and Kotz (1970). Assuming a 5% non-evaluable rate, a sample size of 330 patients is planned for this study.

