The non-invasive (sublingual), pre-programmed, single-dose strength Zalviso System addresses many of the limitations of the current IV PCA systems by reducing programming errors, IV catheter complications and inappropriate use of basal infusions. The Zalviso System is comprised of a disposable bar-coded Cartridge filled with a stack of 40 sufentanil tablets 15 mcg (approximately 2 day supply based on usage), a disposable Dispenser and a reusable, rechargeable Controller. The Zalviso System is designed so that with each actuation by the patient, a single sufentanil tablet will be dispensed sublingually with a manufacturer pre-programmed 20-minute lock-out to avoid overdosing. Furthermore, the Zalviso System has additional safety features of 1) a secure access system comprised of an adhesive patient identification Thumb Tag which uses radio-frequency identification (RFID), 2) an Authorized Access Card with RFID for the healthcare professional (HCP) and 3) a security tether.

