### **3.5 Duration of Study**

After screening, patients may have up to 30 days to begin receiving treatment with study drug. The duration of study treatment administration is at least 24 hours but may extend to 72 hours. The entire study is expected to last approximately nine months from the first patient screened through the last patient's study procedure.

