#### **6.1.4 End of Study**

Patients will be considered completers if they complete the study for a minimum of 24 hours. Patients who are withdrawn from the study for any reason prior to 24 hours will be considered early terminations.

At the time the patient discontinues from the study or a Drug Cartridge is changed, the number of tablets remaining in the Drug Cartridge as displayed on the Zalviso System display screen will be recorded in the source records.

The Patient Usability Questionnaire (Appendix IV) will be completed at the end of the study or at the time of early discontinuation. The Patient Usability Questionnaire will be completed before the patient completes the PGA (Appendix III).

Study staff will complete the Nurse Usability Questionnaire (Appendix V) when they have interacted with 5 patients, or when enrollment is completed at the study site. The study staff will download the controller data after its use by each patient using the data transfer cable and download utility software provided by AcelRx. The data files will then be transferred per AcelRx instructions.

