2.8 Premature Termination from the Study

Patients who prematurely terminate from the study will be summarized according to the reason for termination. Each unique reason will be determined by the investigator.

Patients who prematurely terminated from the study and reasons for not entering next time period will be summarized in Post-text Tables 14.1.3 to 14.1.7.

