2.10.1 Efficacy Variables

The efficacy variables and parameters are:

- (1) Proportion of patients who experienced at least one system-generated error based on the Controller data while using the Zalviso System
- (2) Proportion of patients, if any, with tablet dispensed but not requested
- (3) Proportion of patients, if any, with tablet dispensed when the Zalviso System is in lockout
- (4) Proportion of patients with misplaced tablet(s)
- (5) Number of misplaced tablets (i.e., tablet found outside the patient's mouth)
- (6) Proportion of patients who experienced either a system-generated error or a misplaced tablet (i.e. a dispense failure)
- (7) Assessment of the number of Zalviso System notifications to the nurse to retrain patient to not pull down on Controller while dosing (i.e., mitigation of Error 302)
- (8) Proportion of patients who rate the Patient Global Assessment (PGA) of method of pain control over 24, 48 and 72 hours as "good" or "excellent"
- (9) Proportion of patients who responded in each category of the PGA
- (10) Proportion of Healthcare Professionals who rate the Global Assessment (HPGA) of method of pain control over 24, 48 and 72 hours as "good" or "excellent"
- (11) Proportion of Healthcare Professionals who responded in each category of the HPGA
- (12) Proportion of patients who terminate from the study due to inadequate analgesia over the 24-hour, 48-hour and 72-hour study period
- (13) Time to terminate from the study due to inadequate analgesia
- (14) Time-weighted summed pain intensity difference (SPID) over the 24-hour study period (SPID24), over the 48-hour study period (SPID48), and over the 72-hour study period (SPID72)
- (15) SPID up to each evaluation time point
- (16) Total pain relief (TOTPAR) over the 24-hour study period (TOTPAR24), over the 48-hour study period (TOTPAR48) and over the 72-hour study period (TOTPAR72)
- (17) TOTPAR up to each evaluation time point
- (18) Pain intensity (PI) at each evaluation time point
- (19) Pain intensity difference (PID) at each evaluation time point
- (20) Pain relief (PR) at each evaluation time point
- (21) Patient Usability Questionnaire (PUQ)
- (22) Nurse Usability Questionnaire (NUQ)

- (23) Total number of study drug doses used over 24, 48, and 72-hour study period, average hourly use, and average inter-dosing interval.
- (24) Total amount of supplemental morphine utilized

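### Does the device failure rate need a fixed 24, 48 or 72-hour horizon before its 5% limit can be read?

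*SAP*

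**What the plan says.** SAP 2.1 and Protocol 9.1 define the device dispense failure rate by three kinds of event, all read from the Controller: "This failure rate is the proportion of patients who experienced at least one of following events". The trial passes if the upper limit of the 90% interval is no higher than 5%. SAP 2.10.4 plans one pooled proportion with an exact Clopper-Pearson interval.

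The length of use varies by design. Protocol 3.5: "The duration of study treatment administration is at least 24 hours but may extend to 72 hours". Under Protocol 6.1.4, 24 hours makes a completer and earlier withdrawals are early terminations. SAP 2.10.2 keeps all treated patients in the analysis.

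Other variables in SAP 2.10.1 do carry horizons of 24, 48 and 72 hours: the global assessments, dropout for inadequate analgesia, SPID, TOTPAR and doses used. One is a time-to-event variable, item (13): "Time to terminate from the study due to inadequate analgesia". The device items (1) to (6) have no such horizon. The nearest wording is in item (1), which counts system errors during the patient's own use of the system.

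**The concern.** Each tablet is another chance for the device to fail, so a patient with three days of use has roughly three times the opportunity of a patient with one. An ever/never proportion pooled over unequal use does not separate a reliable device used for long from a less reliable one used briefly. The SAP attaches horizons to secondary pain measures but not to the endpoint that decides success, which looks like an oversight. A reader might take a result below 5% as the risk over a full 72-hour course, which the pass rule does not test. The SAP text also plans no summary that divides failures by hours or tablets.

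**Working it through.** **1. The plan's own figure.** Inputs from SAP 2.1: n = 315, expected rate 2%, boundary 2% + 3% = 5%, one-sided alpha 0.05. The Clopper-Pearson upper limit for x failures is the 0.95 quantile of Beta(x + 1, n − x).

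- x = 9: 9/315 = 2.86%, upper limit 4.93%, pass.
- x = 10: upper limit 5.33%, fail.
- False-pass chance: P(X ≤ 9 | 5%) = 0.0449.
- Power: P(X ≤ 9 | 2%) = 0.8960, against the stated 90%.

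These hold for the proportion as defined, whatever the mix of use times.

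**2. How far actual-use risk and 72-hour risk can differ.** The documents give neither the distribution of use nor the shape of the hazard, so both are assumptions here. With a constant hazard and everyone using the device for h hours, the 72-hour risk is 1 − (1 − p)^(72/h). For p = 9/315:

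| Assumed use | Implied 72-hour risk |
|---|---|
| all 24 h | 1 − 0.97143³ = 8.3% |
| all 48 h | 1 − 0.97143^1.5 = 4.25% |
| all 72 h | 2.86% |

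Equal thirds at 24, 48 and 72 hours give 4.3%. If every failure occurs at first use, the answer is 2.86% for any mix. These are conversions of a point estimate, and they are not bounds: use shorter than 24 hours or a rising hazard would give more than 8.3%.

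**3. The same comparison per tablet.** Protocol 1.1 describes a cartridge as a "stack of 40 sufentanil tablets 15 mcg (approximately 2 day supply based on usage", which is about 20 tablets a day. At a constant risk per tablet, the 5% limit equals −ln(0.95)/20 = 2.6 first failures per 1,000 tablets for 24 hours of use, −ln(0.95)/40 = 1.3 for 48 hours, and −ln(0.95)/60 = 0.85 for 72 hours. The range is three-fold.

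**4. What is already planned.** The exposure side of the comparison is collected and reported:

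- SAP 2.11.1 summarises length of exposure in Table 14.3.1.
- SAP 2.10.1 item (23): "Total number of study drug doses used over 24, 48, and 72-hour study period, average hourly use, and average inter-dosing interval".
- SAP 2.8: "reasons for not entering next time period will be summarized in Post-text Tables 14.1.3 to 14.1.7". Protocol 5.4 makes a system error end both device use and study participation. Protocol 4.4 has no device category for termination, but its catch-all category requires the reason to be specified.
- SAP 2.11 lists suspected technical failures among the safety data, and SAP 2.13 provides by-patient listings.
- Protocol 6.1.4: "The study staff will download the controller data after its use by each patient using the data transfer cable".

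A crude rate per tablet is one planned total divided by another. For example, take an assumed mix of 10% at 12 h, 40% at 24 h, 30% at 48 h and 20% at 72 h. Mean use is 1.2 + 9.6 + 14.4 + 14.4 = 39.6 h, or 33 tablets at 20 a day. Then 33 × 315 = 10,395 tablets, and nine first failures are 0.87 per 1,000.

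**5. Would fixed horizons help?** The natural addition is the cumulative incidence of first failure at 24, 48 and 72 hours, with other ends of use as competing events. With use fully observed, its final value equals the crude proportion by construction. Under the mix in step 4 with a constant hazard, the 72-hour row would read 2.86%, while full 72-hour use at the same hazard carries a risk of 5.2%. A row labelled 72 hours could thus invite the very misreading it was meant to prevent.

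**The case for a change.** The strongest case for a change is that this is the only pass/fail endpoint, that one proportion can describe devices differing three-fold per tablet, and that a sentence with one descriptive table would cost almost nothing. The SAP clearly knows how to set horizons and chose to for lesser variables. Termination tables are an imperfect substitute, because device failure is not a listed reason.

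Part of this stands. The SAP text does lack a fixed horizon and does report exposure apart from failures. The titles of Tables 14.2.1 to 14.2.7 are not given, so the absence of a combined summary can be inferred only from the text.

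The rest does not carry. The time frame is not unstated: item (1) ties errors to the patient's own use, and SAP 2.1 takes all three event types from Controller usage data, so actual use is the natural reading of the composite. The 72-hour reading is a hypothetical reader's, and nothing in either document makes that claim. The three-fold range compares extremes in which everyone has the same length of use, and the documents do not say where the trial would fall between them.

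**Conclusion.** No change to the plan. The endpoint is the risk of at least one device failure over use as it occurs in the trial, a sensible target for a patient-controlled device used for as long as the patient needs it. For that quantity the pass rule (at most 9 of 315), the false-pass chance of 4.5% and the power of 89.6% are all sound.

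The limit is one of interpretation. A pass at 9 of 315 is compatible with a 72-hour risk anywhere from 2.9% to 8.3% between the all-72-hour and all-24-hour cases under a constant hazard, and higher if use is shorter or the hazard rises. The planned exposure and dose summaries will show how much use the rate rests on. An analyst who describes the rate as over actual device use, or who adds failures per 1,000 tablets to the report, is filling in detail. The primary result and its error rates would be the same.

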### **5.4 Managing Suspected Zalviso System Errors and Failures**

Refer to the Healthcare Professional-Instructions for Use (HP-IFU) for complete information on Zalviso System alarm, error and notification messages (HP-IFU to be sent under separate cover).

If during patient use an error message is displayed on the controller screen (e.g., Error 301, Error 302, etc), the error displayed will be recorded in the source record and on the suspected technical failure e-CRF. Per the Zalviso System design, if a system error occurs, the Zalviso System will no longer dispense tablets and must be discontinued. The patient will be discontinued from the study and alternate form of postoperative analgesia per standard practice at the site should be instituted.

If either the patient or the investigator's staff observes that the Zalviso System may not be operating properly during patient use, but there are no notification or error messages displayed on the Zalviso System Controller screen, the Zalviso System will be evaluated for the presence of a technical failure in accordance with the procedures detailed in the Zalviso System HP-IFU. If the Zalviso System is suspected of having a technical failure, the System must be discontinued, the patient discontinued from the study and an alternate form of postoperative analgesia per standard practice at the site should be instituted. In the event any Zalviso System is judged to have a suspected technical failure, the Zalviso System will be sent to AcelRx for evaluation and may not be used further until a review by AcelRx is complete and the System is approved for further use. Suspected technical

failures must be documented in the source and the eCRF.

If a misplaced tablet (i.e. any tablet inadvertently dispensed or found outside of the patient's mouth) is found by a patient or study staff, this must be documented in the source record and eCRF. The tablet must be stored securely until CII study drug accountability is conducted. The study staff should document who found the tablet, when and where the tablet was found, and query the patient to determine the likely cause of the misplaced tablet.

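### The device dispense failure rate is read from Controller data alone, so a system error documented on the eCRF goes uncounted if that patient has no usable Controller file

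*SAP*

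**What the plan says.** The failure rate in SAP 2.1, repeated in Protocol 9.1 and the Protocol Synopsis, is the proportion of patients with at least one of three events: a system-generated error, an unrequested tablet, or a tablet dispensed during lockout. On the source, SAP 2.1 states: "All events listed above will be obtained from the Controller patient usage data". The first efficacy variable in SAP 2.10.1 says the same: "Proportion of patients who experienced at least one system-generated error based on the Controller data while using the Zalviso System".

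Protocol 6.1.4 describes how the data are obtained: "The study staff will download the controller data after its use by each patient using the data transfer cable". It gives no back-up if the download fails.

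Protocol 5.4 sets up a second record. When an error message appears, "the error displayed will be recorded in the source record and on the suspected technical failure e-CRF". Suspected failures without a message also go into the source and eCRF. A System with a suspected technical failure is returned: "the Zalviso System will be sent to AcelRx for evaluation and may not be used further" until the sponsor has reviewed it. SAP 2.11 lists suspected technical failures as a safety data item. No section links that item to the failure rate.

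SAP 2.10.2 puts all enrolled and treated patients in the main efficacy analysis, and its missing-data rules cover only pain intensity and pain relief. SAP 2.1 nevertheless expects some loss: "Assuming a 5% non-evaluable rate, a sample size of 330 patients is planned for this study". Non-evaluable is not defined.

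**The concern.** Take a dosed patient whose Controller displayed a system error, whose site entered that error on the eCRF, and whose Controller data turn out to be missing or unreadable. The event is known and documented, and it belongs to the endpoint's first component. Under the stated source rule it still does not count. The patient either stays in the denominator without an event or leaves the analysis as non-evaluable. Both choices lower the estimated rate, because the patient did have a failure.

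The trial is open-label and single-arm, and it is judged on one criterion, an upper limit no worse than 5%. Without a rule, someone must choose how to classify such patients when the results may already be visible. The events are few, so a small number of reclassified patients can change the conclusion.

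**Working it through.** **Inputs.** From SAP 2.1: n = 315, assumed rate 2%, delta 3% (so a limit of 5%), one-sided alpha 0.05, stated power 90%, 5% non-evaluable, 330 planned. From SAP 2.5 and 2.10.4: a 90% exact Clopper-Pearson interval.

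**Reproducing the plan's figure.** For x failures in n patients the upper limit is the 95th percentile of a Beta(x + 1, n − x) distribution.

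| Failures / patients | Point estimate | Upper limit | Criterion |
|---|---|---|---|
| 6/315 | 1.90% | 3.7% | pass |
| 8/315 | 2.54% | 4.54% | pass |
| 9/315 | 2.86% | 4.93% | pass |
| 10/315 | 3.17% | 5.33% | fail |
| 11/315 | 3.49% | 5.71% | fail |

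The trial therefore passes with 9 or fewer failures. Pr(X ≤ 9) for Binomial(315, 0.05) is 0.045, which is the attained alpha. For Binomial(315, 0.02) it is 0.896, which agrees with the stated 90% power. The enrolment figure also holds approximately: 330 × 0.95 = 313.5. The sample size is not in dispute.

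**Effect of uncounted eCRF errors on one result.**

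- Nine failures in readable files, plus one patient with an eCRF-documented error and no usable file. As a non-failure: 9/315, 4.93%, pass. Dropped: 9/314, 4.95%, pass. Counted: 10/315, 5.33%, fail.
- Eight failures in readable files, plus two such patients. As non-failures: 8/315, 4.54%, pass. Dropped: 8/313, 4.56%, pass. Counted: 10/315, 5.33%, fail.
- At the planned rate, 315 × 0.02 = 6.3, so about 6 failures. Three extra give 9/315 and still pass. Four give 10/315 and fail.

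**Effect if the missing patients did not fail.** With 9 failures read, dropping four non-failing patients gives 9/311, upper limit 4.996% (pass). Dropping five gives 9/310, 5.01% (fail). Losing files for unrelated reasons can therefore move the limit slightly upwards, against the sponsor.

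**Effect on the error rate, under assumption.** The documents give no share of failures with unusable Controller data, so 10% to 30% is assumed purely to show a range. The table gives the chance of passing when the true rate is 5%.

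| Share of failures unread (assumed) | Counted as non-failures | Dropped |
|---|---|---|
| 0% | 4.5% | 4.5% |
| 10% | 9.6% | 9.5% |
| 20% | 18.8% | 17.2% |
| 30% | 33.4% | 27.8% |

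For the non-failure column the formula is Pr(X ≤ 9) with X ~ Binomial(315, 0.05 × (1 − share)). For the dropped column the pass mark is recomputed for each reduced n and averaged over the number dropped.

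**The case against.** The strongest reply is that nothing shows failed Controllers losing their data. A system-generated error is one the Controller itself detects and displays. Protocol 5.4 describes a device that stops dispensing, not one whose memory is gone, and Protocol 5.1.2 lists use history and error monitoring among its functions. If files are lost through a cable fault or a site omission, the loss need not be related to failure. This stands. A reader might infer that the plan systematically favours the sponsor, but the documents do not support that. The direction is established only for patients who did have a failure.

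Controllers can also be read without the download. Protocol 6.1.3 has staff take dose times from the Controller's history log, and a displayed error copied to the eCRF is itself Controller output. SAP 2.1 could be stretched to admit it. A returned System might also yield its log. These are possible routes, but neither document states that either one feeds the endpoint.

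The failures would not vanish from the report, because suspected technical failures are a named safety item and early terminations are summarised by reason. That is true, but the pass/fail criterion would still omit them.

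Finally, a device log is an objective and defensible primary source. This is conceded. It argues for reconciling the eCRF with the log, not for ignoring a documented error when the log is unavailable.

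**Conclusion.** The point holds in a limited form. The source rule for the powered endpoint, applied literally, leaves out a documented system error when the Controller data are unusable, although the record needed to count it is already collected. The effect depends on how close the result is to the cut-off. One such patient reverses a result of 9 failures, and four are needed at about 6. At a true rate of 2%, the chance of exactly 8 or 9 failures is about 19%, so a result near the cut-off is plausible but not the expected case. The frequency of unusable files, and any link to failure, are unknown.

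Two stronger readings should be resisted.

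- A reader might take the 330-to-315 allowance as 15 dosed patients with missing files and add them to 9 failures, giving 24/330 = 7.3% with an upper limit of 10.1%. The allowance also covers enrolled patients who are never dosed, so it is not a count of lost device files, still less of device failures.
- A reader might want every suspected failure or unexplained stop counted in the primary endpoint. Those events lie outside the three in SAP 2.1.

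The point concerns that three-event definition. Variable (6) in SAP 2.10.1 attaches the dispense failure label to a different composite that includes misplaced tablets.

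**What to change.** In Protocol 9.1 and SAP 2.1 and 2.10.4:

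- Make the denominator all dosed patients.
- Count a system-generated error if it appears in either the Controller data or the suspected technical failure eCRF/source record, and reconcile the two before database lock.
- Report how many dosed patients have no usable Controller file.
- Add a sensitivity upper limit that counts dosed patients without a usable file as failures.
- Keep suspected failures without an error message, and stops for unknown reasons, out of the primary endpoint.

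Both records are already collected, so the cost is document wording and minor reconciliation work. The rate may come out slightly less favourable. If every file is usable and the two sources agree, the result does not change.
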